Diagnostic Stewardship for Ventilator Associated Pneumonia

Description of Outcomes and Statistical Analysis Plan

NCT05989269

August 11, 2023

Specific Aim 1: In a cluster-randomized crossover trial among 6 ICUs across 3 medical centers, evaluate the impact of a VAP diagnostic stewardship intervention on antibiotic use, VAP diagnoses, and adverse events.

Hypothesis: We expect a reduction in unnecessary antibiotics for VAP and in VAP clinical diagnoses in the intervention vs. control periods across all sites, without an increase in adverse events.

Primary Outcome: The primary efficacy outcome is reduction in proportion of unnecessary antibiotic therapy for presumed VAP in the intervention (modified reporting) period compared to control (standard reporting period), among patients not meeting clinical criteria for pneumonia and with growth of one or more organism(s) not considered normal upper respiratory flora.

Antibiotic action based on index culture result will be classified as follows:

- a) Not on empiric antibiotic(s), new antibiotic started based on index respiratory culture result, completed course for VAP
- b) Not on empiric antibiotic(s), no new antibiotics initiated based on culture result
- c) On empiric antibiotic(s), changed based on index respiratory culture, completed course for VAP
- d) On empiric antibiotic(s), continued without change following index respiratory culture, completed course for VAP
- e) On empiric antibiotic(s), antibiotics discontinued based on culture results
- f) On empiric antibiotics(s), but this therapy was not directed at the results of the index respiratory culture, and was not directed towards VAP

For patients where culturing was deemed inappropriate, antibiotic use in categories a, c, and d will together be considered “unnecessary antibiotic therapy for presumed VAP”

Note: Multiple respiratory cultures from the same patient may be eligible for intervention i.e., modified reporting during the intervention period. However, clinical outcomes linked to an “index respiratory culture” will be assessed using a single randomly selected respiratory culture from each included patient.

Secondary outcomes are as follows:

1. Antibiotic consumption outcomes: The following three outcomes will be measured to understand the impact on antibiotic use in ICU patients

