 - a. Duration of antibiotic therapy: The duration of antibiotic therapy for possible or presumed VAP among patients who underwent intervention during the intervention period and among patients eligible for intervention in the control period will be compared. Duration of antibiotic therapy will be collected for all categories above (except b), and defined as uninterrupted days of therapy, irrespective of the number of different antibiotics, for the same episode of presumed VAP, assessed at discharge or day 28 whichever occurs first. For patients in category b, duration will be zero.
 - b. Antibiotic consumption during study intervention and control periods will be collected as antibiotic days of therapy (DOTs) as defined by CDC (Centers for Disease Control) NHSN as number of days that patients receive an antibiotic agent during a calendar day. The DOT for a given patient receiving multiple antibiotics on the same calendar day will

be the sum of the DOT for each antibiotic. This will be standardized to patient census of 1,000 patient days.

- i. Unit-level total antibiotic days of therapy (DOT) per 1,000 ICU patient-days: These data will be obtained from the hospital antimicrobial stewardship programs and will be compared in aggregate between the intervention and control periods for all study ICUs combined, and by hospital.
 - ii. Unit-level respiratory antibiotic DOT: This will be captured from the EMR by counting antibiotics that are ordered for “respiratory infection” indication starting at day 3 or later of ICU stay and expressed as days of therapy per 1,000 ICU patient-days. We will validate this outcome by chart review of a small sample of patients. These will be compared in aggregate between the intervention and control periods for all study ICUs combined, and by hospital.
2. Clinical diagnoses of VAP within 7 days after the index culture - measurement of this outcome will help understand how modification of reporting would influence the likelihood of a patient receiving a diagnosis of VAP. Because there are no consensus definitions for VAP, we will use the treating clinician’s documentation of pneumonia or VAP and treatment for those conditions to capture this outcome. The clinical diagnosis of VAP is an intermediate outcome that precedes the endpoint of antibiotic use. Clinical diagnoses of tracheobronchitis within 7 days after the index culture will also be recorded.

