Primary Outcome: The primary efficacy outcome is the reduction in proportion of unnecessary antibiotic therapy for presumed VAP in the intervention period i.e., modified reporting period compared to control period or standard reporting period, among patients not meeting criteria for culture order and with growth of one or more organism(s) not considered normal upper respiratory flora. Antibiotic therapy given for a culture that was collected in a patient not meeting algorithm criteria will be considered unnecessary (dichotomous outcome yes/no). For the primary outcome analysis (and all other patient-level analyses below), a patient will be included once in a given admission and the outcome will be assessed on the basis of a randomly selected qualifying respiratory culture during that admission (termed index respiratory culture). We will estimate the proportion of the primary outcome (i.e., unnecessary antibiotic therapy) in each intervention arm and will compare the two groups using risk difference from a generalized linear mixed model with an identity link function. The main analysis for the primary outcome will be intention-to-treat; a secondary per protocol (as treated) analysis will be done in which any cultures during the intervention period for which a modified report was requested but either the modification was not made, or the report was modified but the full report was released upon provider request or other reason, will not be included in the intervention group.

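### Antibiotic duration counts only unbroken days, so a course stopped and restarted in the same episode is undercounted by a route that only the intervention period has

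*SAP*

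**What the plan says.** Secondary outcome 1a of the SAP gives the duration measure as "defined as uninterrupted days of therapy, irrespective of the number of different antibiotics, for the same episode of presumed VAP". The time limit follows in the same sentence: it is "assessed at discharge or day 28 whichever occurs first". The SAP names no permitted gap, does not say which run counts when there are two, and has no rule for a restart.

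The same duration is used in three places: the negative binomial mixed model (Statistical Methods for Secondary outcomes), the tie-break between patients with the same clinical rank (Aim 2a, Strategy), and the difference in means on the vertical axis of the two-dimensional analysis (Statistical methods for Aim 2a).

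The SAP expects some withheld reports to be released. Secondary outcome 3 tabulates requests for complete reports and notes that they arise only in the intervention period. The per-protocol paragraph under Statistical methods for Aim 1 covers cases where "the report was modified but the full report was released upon provider request". These patients stay in the main intention-to-treat analysis.

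For the primary outcome, category e is "On empiric antibiotic(s), antibiotics discontinued based on culture results". It carries no time point. The event rule is that "antibiotic use in categories a, c, and d will together be considered" unnecessary, so e is a non-event.

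**The concern.** A patient on empiric therapy may be stopped when the modified report arrives and restarted for the same presumed episode after the full report is released. Under an unbroken-days rule, part of that treatment drops out of the count. A control patient receives the full report at once and cannot reach a gap by this route. The definition is worded identically for both periods, but the periods are not equally exposed to what it leaves out.

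The consequence is that delayed treatment can be recorded as avoided treatment. This matters most in Aim 2, whose purpose is to weigh antibiotic exposure against clinical outcome and where a shorter course decides every tie in rank.

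**Working it through.** No figure in the SAP depends on the duration definition, so there is no stated number to reproduce. The sample size rests on the primary outcome and is not affected. The check applies the definition to a sequence and follows the result through.

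**1. One patient (illustrative days, not from the SAP).** Take 3 days of therapy, a gap, then 7 days, all for one episode.

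| Reading | Days scored | Days dropped |
|---|---|---|
| First unbroken run | 3 | 7 |
| Longest unbroken run | 7 | 3 |
| All days of the episode | 3 + 7 = 10 | 0 |

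The SAP wording excludes the third reading and does not choose between the first two.

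**2. Arm mean.** If a share q of an arm has d days dropped, its mean falls by q × d. The shift in the intervention-minus-control difference is −(q_I × d_I − q_C × d_C). Gaps with other causes can occur in both periods. The release route adds to q_I only. For that route alone:

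| Assumed q | First run counted (d = 7) | Longest run counted (d = 3) |
|---|---|---|
| 2% | 0.02 × 7 = 0.14 days | 0.02 × 3 = 0.06 days |
| 5% | 0.05 × 7 = 0.35 days | 0.05 × 3 = 0.15 days |
| 10% | 0.10 × 7 = 0.70 days | 0.10 × 3 = 0.30 days |

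The vertical axis of the two-dimensional analysis moves by the same amount, towards fewer antibiotic days under modified reporting.

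**3. Tie-break.** Compare this patient with a control patient of the same clinical rank who had 8 continuous days (illustrative). Scored 3 or 7, the intervention patient wins the pair. Scored 10, the intervention patient loses it. The definition alone reverses the result of the comparison.

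**4. Primary outcome, texts side by side.** The duration definition does not set the primary yes/no result; the categories do. The stopped-and-restarted patient meets the words of e at the moment of stopping. Two other texts point to an event:
- Category c is "On empiric antibiotic(s), changed based on index respiratory culture, completed course for VAP". Whether a course was completed can be judged only when it is over, and a restart on the released index culture can be read as a change based on that culture.
- Statistical methods for Aim 1 gives a general rule ("Antibiotic therapy given for a culture that was collected in a patient not meeting algorithm criteria will be considered unnecessary (dichotomous outcome yes/no").

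Category a, "Not on empiric antibiotic(s), new antibiotic started based on index respiratory culture result, completed course for VAP", fits less well because the patient was on empiric therapy. The SAP sets no precedence between e and c, but the balance of its text favours counting the restarted course as unnecessary.

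**The case against.** The strongest case on the other side has four parts.

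**The route is assumed.** The SAP says that clinicians may request the full report, not that they stop, wait and restart. A clinician in doubt may continue therapy while requesting release, or start therapy only after it. Neither path creates a gap. This stands: the frequency is unknown, and the route should not be called typical.

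**Control patients can also be stopped and restarted.** This stands too. It limits the claim to the one trigger that control lacks, and the net effect depends on gaps in both arms.

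**Other measures would show the problem.** Unit-level days of therapy include restarted days, requests are tabulated, and released cultures leave the per-protocol intervention group. These would signal that something is happening, but none corrects patient-level duration or the tie-break. The unit-level figures are aggregates, and the per-protocol analysis is a secondary analysis of the primary outcome that removes these patients from the intervention group without counting their therapy. The exploratory label on secondary outcomes lowers the stakes but does not change the measurement.

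**Gap rules often sit in the protocol or the abstraction form.** That would answer a silence. Here the SAP states a rule, and its literal effect is to exclude days.

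A reader might go further and infer that category e closes at the first discontinuation, so that these patients count as successes on the primary outcome. The document does not support this. No text gives e a time point, categories a, c and d turn on a completed course, and the rule in the methods section points the other way.

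**Conclusion.** The point holds for antibiotic duration. As worded, the definition leaves out days after a break in the same episode, and one cause of such breaks is confined to the intervention period. An undercount by that route favours the intervention in the duration model, the RADAR tie-break and the two-dimensional plot.

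The size cannot be established from the SAP. The range of 0.14 to 0.70 days in the intervention mean assumes that 2% to 10% of patients follow the route and that 7 days are lost for each. It is smaller if the longest run is the one counted. The SAP gives no expected mean duration against which to judge these figures. They illustrate a possible bias and do not demonstrate one.

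For the primary outcome, what remains is a clarification: the SAP should say how such a patient is classified. This is a worthwhile and cheap improvement, not a threat to the trial's main result.

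**What to change.** In secondary outcome 1a, define duration as the total number of calendar days on any antibiotic for that presumed VAP episode, including days after a restart, up to discharge or day 28, whichever is earlier. Leave the start point and the handling of categories b and f as they are. Apply the definition identically in both periods, and use it in Aim 1 and throughout Aim 2a.

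Under Primary Outcome, add one sentence: a course stopped and then restarted for the same index culture and completed for VAP counts as unnecessary therapy, with categories a, c and d, and not as e. This brings the category list into line with the methods section.

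The cost is wording in the SAP and the data-collection form, with the same chart review. The downside is that reviewers must judge whether a restart belongs to the same episode, but the present definition already asks this of them.

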Power and Sample Size: For the population of ICU patients for which ordering of a respiratory culture has been determined inappropriate and there is growth of one or more organism(s) not considered normal upper respiratory flora, we test the effect of the diagnostic stewardship intervention on the proportion of antibiotic prescription in a two-period cluster-randomized cross-over design, where an ICU forms a cluster. The outcome follows a binary distribution with 50% probability to receive antibiotic prescription in the control group (pC). In a conservative estimate, we expect that the intervention reduces the probability by $\Delta = 0.15$ (= pC – pI) percentage points. Assuming the within-cluster within-period correlation is $\rho = 0.06$ and the within-cluster between-period correlation is about $\eta = 0.054$ ^{2,3} a total sample size of $N = 350$ in 6 ICUs across both periods is needed to detect an effect of $\Delta = 0.20$ with 85% power, using a generalized linear mixed model with random cluster, period, and cluster-period interaction effect. The computed total N is equivalent to a mean of about 5 patients per ICU per month, which is feasible in our experience. Given the uncertainty in predicting the actual number of patients that will be eligible to receive the intervention per ICU during the fixed 6-month period, we calculated the power for varying range of effect sizes and total N (Table).

Option	Power	Proportion control	Proportion intervention	N patients eligible for intervention per ICU per period*	Within-cluster within-period rho	Within-cluster between-period rho	Total N
1.	90%	50%	35%	30	0.06	0.054	619
2.	85%	50%	35%	30	0.06	0.054	547
3.	80%	50%	35%	30	0.06	0.054	493

4.	90%	50%	30%	30	0.06	0.054	390
5.	85%	50%	30%	30	0.06	0.054	350
6.	80%	50%	30%	30	0.06	0.054	322
7.	90%	50%	25%	30	0.06	0.054	285
8.	85%	50%	25%	30	0.06	0.054	261
9.	80%	50%	25%	30	0.06	0.054	243

Cluster- and participant-level covariates at baseline will be reported within each intervention arm. Adjusted analysis of the primary outcome will be performed as needed to control for differences in possible influential factors between intervention arms at baseline.

Statistical Methods for Secondary outcomes:

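### Secondary outcome 2 is meant to measure VAP diagnosis upstream of antibiotic use, but its capture rule, on the ordinary reading, counts only diagnoses that were also treated

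*SAP*

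**What the plan says.** The definition is item 2 of the secondary outcomes under Specific Aim 1 in the SAP: "Clinical diagnoses of VAP within 7 days after the index culture". Three statements there matter.

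- **Purpose.** The outcome is to show "how modification of reporting would influence the likelihood of a patient receiving a diagnosis of VAP".
- **Capture rule.** Citing the lack of a consensus definition of VAP, the SAP will use the treating clinician's "documentation of pneumonia or VAP and treatment for those conditions to capture this outcome".
- **Place in the causal order.** "The clinical diagnosis of VAP is an intermediate outcome that precedes the endpoint of antibiotic use".

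The Aim 1 hypothesis names diagnosis and antibiotic use as two effects: "We expect a reduction in unnecessary antibiotics for VAP and in VAP clinical diagnoses in the intervention vs. control periods".

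The primary outcome is built from the antibiotic action categories. Among patients whose culture was deemed inappropriate, "antibiotic use in categories a, c, and d will together be considered" unnecessary therapy. Each of those three categories requires that a course for VAP was completed. Category e is outside the primary outcome: "On empiric antibiotic(s), antibiotics discontinued based on culture results".

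The SAP does not say how a documented but untreated patient is counted in outcome 2, and does not define treatment for it. Tracheobronchitis diagnoses, mentioned in the same item, are simply recorded, with no treatment condition.

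**The concern.** An outcome that contains treatment cannot also be a step that comes before treatment. If a patient must be both documented and treated to count, then a clinician who records VAP but withholds antibiotics contributes no diagnosis. The outcome then mixes two things a reporting nudge might change: whether clinicians apply the VAP label, and whether they prescribe once they have applied it.

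What is at stake is interpretation. Aim 1 expects both antibiotics and diagnoses to fall. If both results fall, a reader will take the second as support for the first, although part of that agreement may come from the shared treatment component. The stated question, whether reporting changes the likelihood of a diagnosis, would not be answered cleanly.

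**Working it through.** The SAP gives no figure for this outcome, so there is none to reproduce. The check is a reading of the definition, followed by an illustration at the SAP's own planning rates.

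**Step 1. The definition as a formula.** Let D be documentation of pneumonia or VAP within 7 days, and T be treatment for it.

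- Ordinary reading: outcome = P(D and T).
- Diagnosis alone: outcome = P(D).
- Alternative reading, either source suffices: outcome = P(D or T).

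Only P(D) is free of treatment.

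**Step 2. Inputs.**

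- Control antibiotic rate, from Power and Sample Size: "The outcome follows a binary distribution with 50% probability to receive antibiotic prescription in the control group", so 50%.
- Intervention rate: 35% or 30%. The text of that section gives both 0.15 and 0.20 as the effect, so both are shown.
- Assumption: P(D) is the same in both periods. The SAP gives no documentation rate; 50% to 80% was tried.
- Assumption: every treated patient is documented, so P(D and T) = P(T).
- Assumption: s is the share of the antibiotic effect that consists of empiric therapy stopped early (a move from c or d to e) but still counted as treatment in outcome 2. The SAP does not fix s, so the full range 0 to 1 is shown.

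**Step 3. Result.** Documentation alone falls by 0 points, by assumption. The outcome on the ordinary reading falls by

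fall = (control rate − intervention rate) × (1 − s).

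| s | 50% to 35% | 50% to 30% |
|---|---|---|
| 0 | 15 × 1 = 15 points | 20 × 1 = 20 points |
| 0.25 | 15 × 0.75 = 11.25 | 20 × 0.75 = 15 |
| 0.50 | 15 × 0.50 = 7.5 | 20 × 0.50 = 10 |
| 1 | 15 × 0 = 0 | 20 × 0 = 0 |

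The documentation rate cancels: any common value from 50% to 80% gives the same falls.

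**Step 4. What the upper end implies.** Take 60% documentation in both periods, an assumed value, with s = 0 and the larger effect. Documented but untreated patients are then 60 − 50 = 10 of 60 (17%) in the control period and 60 − 30 = 30 of 60 (50%) in the intervention period. The 20-point figure therefore needs half of the documented patients in the intervention period to go untreated. It is a limit and not an expected value.

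**Step 5. The alternative reading.** If either source suffices and every treated patient is documented, P(D or T) = P(D), and the fall is 0 points. Treatment is still part of the definition, and two abstractors who read the rule differently would code a documented but untreated patient differently.

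**The case against.** The strongest reply is that the sentence never says treatment is required. It can be read as naming two chart sources, and on that reading the artefact in the illustration disappears. That stands as a possibility, but the SAP does not say it, and the conjunctive reading is the ordinary one. The rule needs settling in either case.

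Second, the choice has a reason. With no consensus definition, asking for treatment helps to separate a working diagnosis from a rule-out entry. This supports reporting a documented-and-treated result. It does not support describing that result as a diagnosis that precedes antibiotic use.

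Third, a reader might infer that outcome 2 simply repeats the primary outcome, or that any effect on treatment must show up as an effect on diagnosis. The SAP does not support either inference. Categories a, c and d need a completed course, whereas outcome 2 asks for treatment without that condition and adds documentation, which the primary definition does not mention. A shift from c or d to e lowers the primary outcome and may leave outcome 2 unchanged.

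Fourth, a reader might infer that an analysis of the path from diagnosis to treatment is lost. The SAP plans no such analysis. It also treats secondary outcomes as exploratory, without multiplicity adjustment. Both facts limit the consequence.

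**Conclusion.** The point holds as an inconsistency between what outcome 2 is for and how it is captured. On the ordinary reading, treatment sits inside an outcome that the SAP places before treatment, so reduced treatment among documented patients can be read as fewer VAP diagnoses, and concordance with the primary outcome is partly built in.

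The size is open. The range of 0 to 15 points, or 0 to 20 at the larger planned effect, rests on equal documentation in both periods, every treated patient being documented, and the conjunctive reading. Where the trial would fall depends on how much of the antibiotic effect is early stopping and on whether stopped therapy counts as treatment, which the SAP leaves undefined. It would be wrong to conclude that a spurious 20-point fall is to be expected.

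The primary outcome, its analysis and the sample size are untouched. The change is still worth making before the outcome analysis, because fewer VAP diagnoses is a named part of the Aim 1 hypothesis.

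**What to change.** Amend item 2 of the secondary outcomes as follows.

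1. Make the diagnosis outcome clinician-documented pneumonia or VAP within 7 days after the index culture, recorded as an assessed diagnosis and not a rule-out entry, whether or not it was treated.
2. Report documented-and-treated beside it as a separate component, so that documented-but-untreated patients are visible in each period.
3. State, for that component, whether empiric therapy that was stopped counts as treatment.

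The cost is SAP wording and an abstraction rule for what counts as an assessed diagnosis. The capture rule already draws on both documentation and treatment, so no new source of data is needed, and the design and sample size do not change. The drawback is that documentation alone is somewhat less specific. Showing the documented-and-treated result next to it addresses this.

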 - a. We will perform a sensitivity analysis of the impact on antibiotic use outcomes after excluding patients diagnosed with tracheobronchitis within 7 days of index culture. The hypothesis is that the intervention will have limited impact on those diagnosed and treated for ventilator-associated tracheobronchitis, and thus, we may see a larger difference between intervention and control when excluding patients with diagnoses of tracheobronchitisVentilator-free days: Ventilator-free days is defined as the number of calendar days within 28 days after the index respiratory culture on which the patient was not mechanically ventilated. Any patient dying within 28 days of the index respiratory culture collection will be assigned zero ventilator-free days. Ventilator-free days will be compared between the intervention and control periods for all study ICUs combined, and by hospital.
3. Rate of requests for complete reports in the intervention period – these data are applicable in the intervention period only. This will be a primarily descriptive analysis to help us understand if the intervention worked as intended i.e., how frequently did clinicians still want the full report with organism identification despite the nudge to consider asymptomatic colonization.
4. Adverse event outcomes: Death, bacteremia, and septic shock (from any cause) within 7 days of the index culture order will be recorded as potential significant adverse events from a delayed or missed true VAP diagnosis or delay in initiation of appropriate antimicrobial therapy, similar to methods described by Daley et al.¹ Incidence of these events will be compared between intervention and control periods individually for each event, and as a combined adverse event outcome. Two-person adjudication will be used to determine whether the above events were attributed to the intervention, during the intervention period.

Statistical methods for Aim 1:

Descriptive analyses using the Wilcoxon rank-sum test for continuous variables and the chi-square or Fisher’s exact tests for categorical variables will be used to compare patient-level data across each intervention arm. Analyses will be conducted on an intention-to-treat basis and will account for the cluster-randomized crossover design to ensure correct type I error rates and confidence intervals (CIs). A significance level of 0.05 will be used for all statistical comparisons.

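### The tracheobronchitis sensitivity analysis excludes patients by a diagnosis that modified reporting could plausibly change, so a larger difference after exclusion cannot support its hypothesis

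*SAP*

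**What the plan says.** Under Specific Aim 1, secondary outcome 2, the SAP counts clinician diagnoses of VAP in the week after the index culture, in order to learn "how modification of reporting would influence the likelihood of a patient receiving a diagnosis of VAP". It adds: "The clinical diagnosis of VAP is an intermediate outcome that precedes the endpoint of antibiotic use". On the companion diagnosis it says: "Clinical diagnoses of tracheobronchitis within 7 days after the index culture will also be recorded".

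Item 2a then repeats the antibiotic-use analyses "after excluding patients diagnosed with tracheobronchitis within 7 days of index culture". The reason given is that "the intervention will have limited impact on those diagnosed and treated for ventilator-associated tracheobronchitis", and the expected result is that "we may see a larger difference between intervention and control when excluding patients" with that diagnosis.

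The general rule under Statistical methods for Aim 1 is: "Analyses will be conducted on an intention-to-treat basis and will account for the cluster-randomized crossover design". Item 2a neither states nor checks that the tracheobronchitis share is the same in both periods, and it gives no caution on how to read the result.

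**The concern.** The exclusion uses a clinician's label that can be given after assignment and after the report. The SAP places the neighbouring label, VAP, on the pathway from report to antibiotic. A clinician who is steered away from VAP may write colonisation, no diagnosis, or tracheobronchitis. If the last becomes more or less frequent under modified reporting, different kinds of patients are removed from the two periods, and those who remain are no longer comparable.

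The SAP's rationale does not deal with this. Limited impact on antibiotic use among patients who already carry the diagnosis says nothing about whether the diagnosis is given equally often in both periods.

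What is at stake is the reading of a prespecified analysis with a stated direction. A larger difference after exclusion could come from the mechanism the SAP describes or from a shift in labelling, and the analysis cannot tell the two apart.

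**Working it through.** **Inputs from the SAP (Power and Sample Size).** Control proportion 50%; differences of 15 and 20 points discussed in the text. The SAP gives no figure for analysis 2a and no tracheobronchitis rate, so every tracheobronchitis share below is an assumption.

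**The SAP's own sample size.** For 50% vs 30%, 85% power, 30 patients per ICU per period and correlations 0.06 and 0.054, the design effect is 1 + 29 × 0.06 − 30 × 0.054 = 1.12. With two-sided 5% significance, 2 × (1.960 + 1.036)² × (0.25 + 0.21) / 0.20² × 1.12 = 231.3. Adding 4 × 30 = 120 gives 351.3, against 350 stated. The added 120 is inferred from the table; the SAP does not state it. No tracheobronchitis share enters, so this calculation is untouched by the point.

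**Formula for the exclusion.** Let t be the proportion of all patients in an arm with the event, q the share diagnosed with tracheobronchitis, and b the fraction of those who count as events. After exclusion the proportion is

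p = (t − q × b) / (1 − q).

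**Main illustration: no true effect.** t = 50% in both arms, b = 1, q = 5% control and 15% intervention.

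- Control: (0.50 − 0.05) / 0.95 = 47.4%
- Intervention: (0.50 − 0.15) / 0.85 = 41.2%
- Difference: a false fall of 6.2 points

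**Range of assumed shares** (differences are intervention minus control, in points).

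| Scenario | Control share | Intervention share | Difference after exclusion |
|---|---|---|---|
| True difference 0, b = 1 | 10% | 5 / 10 / 15 / 20 / 25% | +2.9 / 0.0 / −3.3 / −6.9 / −11.1 |
| True difference 0, b = 0 | 10% | 0 / 5 / 10 / 15 / 20% | −5.6 / −2.9 / 0.0 / +3.3 / +6.9 |
| True difference −20 (50% vs 30%), b = 1 | 20% | 20 / 15 / 10 / 5 / 0% | −25.0 / −19.9 / −15.3 / −11.2 / −7.5 |

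- *Created.* In the two null scenarios the difference is zero only when the shares are equal.
- *Masked.* In the third row, equal shares give the larger difference that the SAP expects (20 / 0.80 = 25.0). A fall in the share from 20% to 5% reduces it to 11.2: 0.30 / 0.80 = 37.5% vs 0.25 / 0.95 = 26.3%.
- *Enlarged.* With 50% vs 30%, b = 1 and shares of 10% and 20%, the result is 0.40 / 0.90 = 44.4% vs 0.10 / 0.80 = 12.5%, a difference of −31.9. Equal shares of 10% give 44.4% vs 0.20 / 0.90 = 22.2%, or −22.2.

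**Whether b is 1 or 0 is not settled.** The Primary Outcome definition counts categories a, c and d, each of which requires a completed course for VAP; a tracheobronchitis course would then not be an event. The Primary Outcome paragraph under Statistical methods for Aim 1 is broader and counts antibiotics given for a culture in a patient outside the algorithm criteria; a tracheobronchitis course could then be an event. With shares of 5% and 15%, 50% with a VAP event in both arms and b = 0, the result is 0.50 / 0.95 = 52.6% vs 0.50 / 0.85 = 58.8%, a false rise of 6.2 points.

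**Outcomes that keep everyone, in the main illustration.** Antibiotics for VAP or tracheobronchitis: 50% vs 50%, the correct answer. Antibiotics for VAP only: 50 − 5 = 45% vs 50 − 15 = 35%, a false fall of 10 points from relabelling alone.

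**The case against.** The case for leaving item 2a alone has several parts, and some of them stand.

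- *Reach.* This is a labelled sensitivity analysis. The main primary analysis keeps these patients, and the SAP calls its secondary results exploratory. That stands, although the exploratory label is given because of multiple comparisons and does not address selection.
- *What the SAP says about labels.* A reader might infer that the SAP expects reporting to change tracheobronchitis diagnoses. It says this only of VAP. That the tracheobronchitis share could move is a plausible inference, not a stated fact.
- *Timing.* A reader might take the diagnosis as always following the report. The window runs from the index culture, so some diagnoses may precede the report, and the reporting of that culture cannot change those. The later ones are enough for the bias to arise.
- *Intent.* A reader might infer that a larger difference would be declared a confirmation. The SAP attaches no such rule; it says only that a larger difference may be seen.
- *Size.* The 6.2 points need a threefold difference in label share, no true effect and treatment of every labelled patient. With equal shares the null bias is zero. This stands: the figure is an illustration, not an estimate.
- *Alternatives.* Keeping everyone but counting only VAP courses is worse in the main illustration (10 points against 6.2). If the narrower event definition governs, and treated patients are merely relabelled, the full-set result is already 45% vs 35% and the exclusion shrinks that false effect to 6.2 points. This stands, and it rules out a VAP-only outcome shown alone. It does not apply to the combined outcome.

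**Conclusion.** The point holds in a limited form. Item 2a conditions on a post-assignment diagnosis that can follow the report and that reporting could plausibly shift. If the tracheobronchitis share differs between periods, the exclusion can create, enlarge or mask a difference, so a larger difference after exclusion is not evidence for the stated hypothesis.

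The size is unknown because the SAP gives no rates. Under assumed shares that differ by 10 points and no true effect, the false difference is about 6 to 7 points, and its sign depends on which arm has the larger share and on whether tracheobronchitis courses are events. It would be tempting to set this beside the planned 15 to 20 points as a threat to the trial's main result. The SAP does not support that reading, since neither the main intention-to-treat comparison nor the sample size depends on item 2a.

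**What to change.** Replace the exclusion in item 2a with an analysis that keeps every patient in the intention-to-treat set and takes antibiotics for VAP or tracheobronchitis as the outcome. Beside it, compare the tracheobronchitis diagnosis rate between arms as an outcome in its own right, so that any shift in labelling can be seen.

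A VAP-only outcome may be shown, but only next to the combined one, because relabelling alone can move it.

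If the exclusion is kept, label it descriptive and state that a larger difference will not be read as confirming the hypothesis.

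The cost is SAP wording, one extra model, and a record of whether a course was given for tracheobronchitis. That last item is additional data: the SAP already records the diagnosis per patient, but categories a to f do not identify a course given for tracheobronchitis.
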